11.2. Secondary endpoints

Efficacy

VE, in subjects receiving the 1790GAHB vaccine vs. placebo, will be also measured during inpatient stay (Day 57 to Day 64) against:

- Rate of shigellosis *as defined by* the CHIM working group case definition for shigellosis occurring within a period starting with challenge visit and lasting until the end of the inpatient stay, in all subjects. (*Amended: 23 July 2019*)
- Rate of shigellosis, as defined by: severe diarrhea OR moderate diarrhea with fever or with one or more moderate constitutional/enteric symptom OR dysentery [[≥2 loose stools with gross blood (hemoccult positive) in 24 hours] AND [≥1 reportable constitutional/enteric symptom]].
- Rate of more severe shigellosis as defined by: severe or moderate diarrhea with fever or with one or more severe constitutional/enteric symptom OR dysentery [[≥2 loose stools with gross blood (hemoccult positive) in 24 hours] AND [*oral temperature* ≥38.0°C OR ≥1 severe constitutional/enteric symptom]]. (Amended: 23 July 2019)
- Shedding of *S. sonnei* strain 53G.
 - Shedding of *S. sonnei* strain 53G is defined as positivity of at least one stool sample either by culture or qPCR or both.
- Severe diarrhea
- More severe diarrhea.
- Dysentery.

205626 (S SONNEI MONO GMMA SBVGH-003 [H03_03TP])
Protocol Amendment 6 Final

- Weight of all grade 3-5 stools.
- Total number of all grade 3-5 stools.
- Confirmed S. sonnei 53G shedding AND moderate or severe diarrhea OR dysentery OR presence of oral temperature ≥ 38.5 °C OR presence of one or more severe intestinal symptoms (abdominal pain, cramping, nausea, vomiting, gas, anorexia).
- Disease not fulfilling the protocol primary case definition for shigellosis associated or not with mild to moderate symptoms including: passing loose stool (not meeting the protocol definition of moderate or severe diarrhea), abdominal pain, abdominal cramps, gas, anorexia, nausea, headache, myalgia, malaise, arthralgia, fever, vomiting and IV fluid administration.
- Time to onset of shigellosis after challenge, according to the protocol primary case definition.

Safety

Solicited adverse events

• Occurrence of each solicited local and systemic adverse event within 7 days after each vaccination.

Unsolicited adverse events

• Occurrence of unsolicited AEs within 28 days after vaccination and after challenge, according to Medical Dictionary for Regulatory Activities (MedDRA) classification.

Serious adverse events

• Occurrence of all SAEs and related SAEs from Day 1 to study end.

Adverse events of special interest

• Occurrence of AESI (i.e., symptomatic neutropenia) from Day 1 to study end.

Laboratory parameters

• Out of laboratory reference range and/or clinically significant value (according to local ranges) for hematology at 7 days after first and second vaccination and at last study visit (Visit 8).

Immunogenicity

The measures of immunogenicity, against the LPS of S. sonnei, will include:

- IgG geometric mean concentrations (GMCs) pre-vaccination (Day 1), 7 and 28 days after first and second vaccination by antibody concentration at baseline (i.e., above vs. below the assay detection limit), as determined by anti-S. sonnei LPS IgG ELISA.
- IgG GMC pre-challenge (Day 57), 7 and 28 days after challenge (Day 64 and Day 85) as determined by anti-*S. sonnei* LPS IgG ELISA.
- Number and percentage of subjects achieving a post vaccination anti- S. Sonnei LPS concentration ≥ 121 EU/ml at 28 days after first and second vaccination.

205626 (S SONNEI MONO GMMA SBVGH-003 [H03_03TP])
Protocol Amendment 6 Final

• Number and percentage of seroresponders* for anti-S. sonnei LPS at 28 days after first and second vaccination.

*Seroresponse is aimed to define a significant increase in anti *S. sonnei* LPS IgG concentration in post-vaccination samples and relies on the definition already used in a previous phase II study in Kenyan population. For the purpose of this study seroresponse is defined as:

- If the baseline value is greater than 50 EU/mL then an increase of at least 50% in the post-vaccination sample as compared to baseline.
- If the baseline value is less or equal to 50 EU/mL then an increase of at least
 25 EU/mL in the post-vaccination sample as compared to baseline.

Note: Threshold values/increases given in the definition of seroresponse might be subject to change during the course of the study (e.g., in case of optimization/qualification/validation of the anti S. sonnei LPS IgG ELISA).

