2.2. Secondary objectives

Efficacy

- To determine the efficacy of the 1790GAHB vaccine compared to placebo against:
 - Shigellosis as defined by the CHIM expert working group on case definition.*
 - Shigellosis, as defined by: severe diarrhea OR moderate diarrhea with fever or with one or more moderate constitutional/enteric symptoms OR dysentery [[≥2 loose stools with gross blood (hemoccult positive) in 24 hours] AND [≥1 reportable constitutional/enteric symptom]].
 - More severe shigellosis, as defined by: severe or moderate diarrhea with fever or with one or more severe constitutional/enteric symptoms OR dysentery [[≥2 loose stools with gross blood (hemoccult positive) in 24 hours] AND [oral temperature ≥38.0°C OR ≥1 severe constitutional/enteric symptom]]. (Amended: 23 July 2019)
 - Shedding of S. sonnei strain 53G.
 - Severe diarrhea.
 - More severe diarrhea.
 - Dysentery.
 - Weight of all grade 3-5 stools.
 - Total number of all grade 3-5 stools.
 - Confirmed S. sonnei 53G shedding AND moderate or severe diarrhea OR dysentery OR presence of oral temperature ≥ 38.5°C OR presence of one or more severe intestinal symptoms (abdominal pain, cramping, nausea, vomiting, gas, and anorexia).

205626 (S SONNEI MONO GMMA SBVGH-003 [H03_03TP])
Protocol Amendment 6 Final

- Disease not fulfilling the protocol primary case definition for shigellosis
 associated or not with mild to moderate symptoms including: passing loose stool
 (not meeting the protocol definition of moderate or severe diarrhea), abdominal
 pain, abdominal cramps, gas, anorexia, nausea, headache, myalgia, malaise,
 arthralgia, fever, vomiting and IV fluid administration.
- Time to onset of shigellosis after challenge, according to the primary case definition.
- *According to the working group, the participant must fulfil any one of the three following possible endpoints to qualify as having reached the CHIM case definition for this objective:
- 1. Severe diarrhea defined as [≥6 loose stools in 24 hours] OR [>800 grams loose stools in 24 hours]
- 2. Moderate diarrhea defined as [4-5 loose stools in 24 hours OR 400-800 grams loose stools in 24 hours] AND [oral temperature ≥38.0°C OR ≥1 moderate constitutional/enteric symptom OR ≥2 episodes of vomiting in 24 hours]
- 3. Dysentery defined as [≥2 loose stools with gross blood (hemoccult positive) in 24 hours] AND [oral temperature ≥38.0°C OR ≥1 moderate constitutional/enteric symptom OR ≥2 episodes of vomiting in 24 hours].

Safety

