4.3. Shigellosis

For the primary and secondary objectives in the challenge phase of the study, the protocol primary case definition for shigellosis is:

• Shedding of *S. sonnei* 53G accompanied by moderate or severe diarrhea OR shedding with an oral temperature of ≥ 38.5 °C).

For the secondary objectives in the challenge phase of the study, 2 definitions of shigellosis are used:

- 1. CHIM working group case definition for shigellosis as defined by any one of the three following possible endpoints:
 - Severe diarrhea defined as [≥6 loose stools in 24 hours] OR [>800 grams loose stools in 24 hours]
 - Moderate diarrhea defined as [4-5 loose stools in 24 hours OR 400-800 grams loose stools in 24 hours] AND [oral temperature ≥38.0°C OR ≥1 moderate constitutional/enteric symptom OR ≥2 episodes of vomiting in 24 hours]
 - Dysentery defined as [≥2 loose stools with gross blood (hemoccult positive) in 24 hours] AND [oral temperature ≥38.0°C OR ≥1 moderate constitutional/enteric symptom OR ≥2 episodes of vomiting in 24 hours].
- 2. Shigellosis as defined by any one of the three following possible endpoints:
 - Severe diarrhea defined as [≥6 loose stools in 24 hours OR >800 grams loose stools in 24 hours]
 - Moderate diarrhea defined as [4-5 loose stools in 24 hours OR 400-800 grams loose stools in 24 hours] AND [oral temperature ≥38.0°C OR ≥1 moderate constitutional/enteric symptom].
 - Dysentery defined as [≥2 loose stools with gross blood (hemoccult positive) in 24 hours] AND [≥1 reportable constitutional/enteric symptom].

For the secondary objectives in the challenge phase of the study, more severe shigellosis is defined by any one of the two following possible endpoints:

- Moderate OR severe diarrhea [≥4 loose stools in 24 hours OR ≥400 grams loose stools in 24 hours] AND [oral temperature ≥38.0°C OR ≥1 severe constitutional/enteric symptom].
- Dysentery defined as [≥2 loose stools with gross blood (hemoccult positive) in 24 hours] AND [oral temperature ≥38.0°C OR ≥1 severe constitutional/enteric symptom]. (Amended: 23 July 2019)

205626 (S SONNEI MONO GMMA SBVGH-003 [H03_03TP])
Protocol Amendment 6 Final

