11.4. Determination of sample size

Primary objective - Efficacy

In comparing the protective efficacy of 1790GAHB vaccine against the placebo group the following assumptions will be made:

Assuming a true VE of 70%, a total number of 21 confirmed cases will be needed to demonstrate that the LL of the two-sided 90% CI for the VE is above 0% with 80% power (by Pass 2013, One Proportion Power Analysis, one-sided test, one-sided alpha = 5%).

Based on the results obtained by the Cincinnati Children's Hospital Medical Center, where the challenge model was developed, in subjects receiving a challenge with 1500 CFU of *S. sonnei* 53G, the attack rate for the primary case definition of this study is 58%. Thus considering an AR of 58% in the placebo group and a percentage of non-evaluable subjects of 22%, approximately 72 subjects (36 per group) will be recruited to reach these 21 cases.

The assumption on the value of true VE is based on the percentage of subjects with seroresponse observed in previous studies where the 1.5/25 µg OAg/protein dose of 1790GAHB vaccine was evaluated. In the phase I study in Europe, the observed percentage of subjects with seroresponse was 63% and 88% after 1st and 2nd vaccination respectively. In the Phase IIa study, conducted in endemic region, the observed percentage of subjects with seroresponse was 68% and 90% after 1st and 2nd vaccination, respectively.

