11.8. Analysis of efficacy

VE will be evaluated at the end of study period. VE will be estimated as 1-RR where RR is the risk ratio (proportion of subjects reporting the disease in the vaccinated group over the proportion in the placebo group) together with 90% CIs.

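### Vaccine efficacy computed as 1-RR against disease that falls short of the primary case definition cannot be read as efficacy, because primary cases are barred from the endpoint but stay in the denominator

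*Protocol*

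**What the plan says.** Section 2.2 introduces the secondary efficacy list with "To determine the efficacy of the 1790GAHB vaccine compared to placebo against". One item is disease that does not meet the primary definition, with or without a set of mild to moderate symptoms. Section 11.2 repeats the item as an endpoint: "Disease not fulfilling the protocol primary case definition for shigellosis associated or not with mild to moderate symptoms", followed by symptoms such as gas, nausea, headache and malaise. Shedding is not required. The sentence that governs the list is "VE, in subjects receiving the 1790GAHB vaccine vs. placebo, will be also measured during inpatient stay (Day 57 to Day 64) against".

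Section 11.8 supplies the estimator: "VE will be estimated as 1-RR where RR is the risk ratio (proportion of subjects reporting the disease in the vaccinated group", divided by the same proportion under placebo, with 90% confidence intervals. It gives no other VE estimator and no separate denominator for this endpoint.

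The primary case definition in section 4.3 is shedding "accompanied by moderate or severe diarrhea OR shedding with an oral temperature of" at least 38.5°C. Section 11.11 makes comparisons without a predefined success criterion descriptive.

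**The concern.** The endpoint, called milder disease here for short, is a middle category: worse than no disease, better than a primary case. It excludes the primary endpoint by definition. A vaccine that turns a primary case into a milder illness adds an event to the vaccine arm. A vaccine that prevents a primary case outright adds a subject who can still be counted for gas or headache. Both are benefits, and both push the risk ratio up.

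The VE printed for this endpoint would therefore combine two things that cannot be separated afterwards: the effect of the vaccine on milder disease, and the larger share of non-cases in the vaccine arm. The better the vaccine works on the primary endpoint, the larger the second part. A strongly negative secondary VE could then stand beside a positive primary result for a reason built into the definition.

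**Working it through.** **Inputs from section 11.4.** Placebo attack rate 58%; true VE 70% (RR 0.30); 36 per group; 22% non-evaluable; one-sided alpha 5%; 80% power. The plan states: "Assuming a true VE of 70%, a total number of 21 confirmed cases will be needed".

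**Assumption, not in the protocol.** q_p and q_v are the shares of non-primary-cases with milder disease in the placebo and vaccine arms. They are varied below.

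**1. Reproducing the plan's figures.** Conditional on the total number of cases, the expected share in the vaccine arm is 0.30/1.30 = 0.231, against 0.5 under no effect. With 21 cases the exact test rejects at 6 or fewer vaccine cases: alpha 0.039, power 0.808. The number needed is 21/(0.58 + 0.174) = 27.9 evaluable per arm, and 27.9/0.78 = 35.7, so 36 per arm. The design figures hold. Evaluable subjects are 36 × 0.78 ≈ 28 per arm.

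**2. Who can still have the secondary endpoint.** Vaccine attack rate: 0.58 × 0.30 = 0.174. Non-cases: placebo 1 - 0.58 = 0.420; vaccine 1 - 0.174 = 0.826. Ratio: 0.826/0.420 = 1.97.

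**3. The estimate.**

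VE = 1 - (0.826 × q_v)/(0.420 × q_p)

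| q_v/q_p | VE |
|---|---|
| 1.00 | -97% |
| 0.75 | -48% |
| 0.60 | -18% |
| 0.508 | 0% |
| 0.40 | +21% |
| 0.30 | +41% |

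Break-even is 0.420/0.826 = 0.508. To show no more than VE = 0, the vaccine must cut milder disease among non-cases by about 49%.

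**4. Dependence on the primary effect, with q_v = q_p.** True VE 30%: 1 - 0.594/0.42 = -41%. True VE 50%: 1 - 0.71/0.42 = -69%. True VE 70%: -97%.

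**5. Two limiting mechanisms at the same primary VE of 70%.**
- All-or-none protection (70% of vaccinees symptom-free, the rest as placebo): vaccine risk is 0.30 × 0.42 × q_p, so VE = +70%.
- Every averted case becomes milder disease and nothing else changes: vaccine risk is 0.42 × q_p + 0.406. VE is -97% at q_p = 1.0, -193% at 0.5 and -322% at 0.3.

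**6. Precision with 28 per arm and equal q.** Approximate log-RR 90% intervals: -299% to +3% at q = 0.5, and -241% to -13% at q = 0.7.

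**7. The cumulative endpoint (primary case or milder disease).** With equal q, VE = 1 - (0.174 + 0.826q)/(0.58 + 0.42q): 40% at q = 0.3, 26% at 0.5, 14% at 0.7, 0% at 1.0. Under pure downgrading it is 0%; under all-or-none protection it is +70%. It does not turn negative in any of these scenarios.

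**The case against.** Five points can be made for the plan.

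- **The sign is not determined.** The -97% needs a vaccine with 70% efficacy against primary cases and no effect on milder disease among non-cases. The protocol gives no such rate. This stands: the estimate can be positive.
- **Established harm is not shown.** A reader might round the expected counts at q = 0.5 (11.56 and 5.88 of 28) to 12 and 6, obtain a Miettinen-Nurminen 90% interval of -306% to -2%, and infer apparent harm. With unrounded counts the interval is -304% to +1%, and q = 0.5 is itself assumed. This stands too.
- **Section 11.8 is a short general statement.** It cannot govern stool weight, stool number or time to onset, which are in the same list, and the item does not say whether counting is by subject or by episode. A statistical analysis plan could add detail. This stands in part: occurrence of disease is a proportion-type endpoint, VE is its stated measure, and 1-RR is the only VE estimator given. A plan faithful to the protocol would produce this estimate.
- **The comparison is descriptive and is one of twelve secondary efficacy items.** This limits the damage, but the label does not make the number a measure of efficacy.
- **Other reporting would show attenuation.** Section 11.10 summarises post-challenge solicited events by maximal severity and group without removing primary cases. That helps a careful reader but leaves the VE in the table.

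**Conclusion.** The point holds, at moderate severity, for a secondary endpoint. As written, 1-RR on this category is not interpretable as efficacy: at one and the same primary VE of 70% it can be +70%, about -97% or as low as -322%, depending on what happens to averted cases and on a background rate that the protocol does not give. The -97% rests on three things: subject-level counting with primary cases kept in the denominator, the protocol's 58% and 70%, and equal risk of milder disease among non-cases. Because the listed symptoms are non-specific and shedding is not required, part of that risk may be untouched by vaccination, which makes a negative value plausible.

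A reader might infer that an effective vaccine is bound to appear harmful here. The protocol does not support that; a reduction of more than about 49% in the conditional risk gives a positive estimate. The primary endpoint, its success criterion, alpha and sample size are not touched.

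**What to change.** In sections 2.2 and 11.2 and the matching synopsis items:

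1. Report milder disease only as counts and percentages by group, beside the primary-case counts, without a VE. State that counting is by subject.
2. Add a cumulative endpoint, any disease after challenge (primary case or milder), and compute VE for it as 1-RR under section 11.8.
3. Optionally, compare an ordered outcome (none, milder disease, primary case) between groups.

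The cost is a few lines of text and the matching table; no new data are needed. The downside is that the cumulative endpoint hides attenuation: it gives 0% if every averted case becomes milder, and it loses contrast if non-specific symptoms are common. That is why the category counts, or the ordered comparison, belong beside it. Restricting the denominator to non-cases is not a remedy, because it conditions on an outcome that arises after randomization.

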1.3.1. Risk assessment

Important Potential/Identified Risk	Data/Rationale for Risk	Mitigation Strategy
	Investigational vaccine: 1790GAHB va	accine
Symptomatic Neutropenia	Eight cases of Grade 2 or Grade 3 neutropenia were reported from Phase 1 clinical trials (asymptomatic). All cases occurred in the first 20	Exclusion criteria for this clinical study include: • Subjects with a low baseline neutrophil count below 1800 cells/µL (LLN).
	days after administration of first vaccine dose, and reversed after discontinuation.	 Previous history of Benign Ethnic Neutropenia, or drug related Neutropenia. Concomitant treatment with
	Literature review of reports of neutropenia in association with vaccination indicates factors noted to be associated with neutropenia (including ethnicity, and low baseline counts) with the majority of cases detected within 2 weeks of the vaccination. None of the reported cases was clinically symptomatic.	neutropenic agents. Monitoring for this clinical study to include: Baseline neutrophil counts. Full blood counts with differential measured at 7 days post each scheduled vaccination. Assessment of clinical impact of neutropenia. Subjects will be closely monitored
	Five cases of asymptomatic neutropenia (Grade 1 and 2) have been reported at Day 7 after receipt of the first dose in 5 subjects.	during the entire study and have hematology repeated every 7 days when neutropenia is identified until resolution. If a case of neutropenia does not resolve based on most recent available laboratory results, before the
	One of the 5 subjects had an additional Grade1 neutropenia episode at Day 28, and another one had two additional episodes, one of which was Grade 3 (940 cells/mL) at 7 days after the second dose and the second was Grade 2 (1,410 cells/mL) at 28 days after second vaccination. All cases were resolved before last study visit.	second vaccination, or challenge agent administration, the subject will not be revaccinated or administered the challenge agent.

205626 (S SONNEI MONO GMMA SBVGH-003 [H03_03TP]) Protocol Amendment 6 Final

	Protocol Amendment 6 Fin								
Important Potential/Identified Risk	Data/Rationale for Risk	Mitigation Strategy							
	Study Procedures								

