groups	Subjects		Screening	1st and 2nd vaccination	Challenge			
S. sonnei	36	18 years – 50 years	Х	х	Х			
Placebo	36	18 years – 50 years	Х	х	Х			

Table 2 Study groups and treatment foreseen in the study

Treatment name	Vaccine/ placebo/	Study Groups					
Treatment name	challenge agent name	S. sonnei	Placebo				
S. sonnei	1790GAHB	X					
Placebo	GAHB-Placebo		Х				
Challenge	S. sonnei 53G strain	Х	Х				

• **Control:** Placebo control with GAHB-Placebo with the same composition as the vaccine except the active ingredient. GAHB-Placebo will also be used as diluent for bedside mixing of the vaccine.

205626 (S SONNEI MONO GMMA SBVGH-003 [H03_03TP])
Protocol Amendment 6 Final

- Vaccination schedule: Subjects will receive 2 doses of either the study vaccine or placebo 28 days apart. At 28 days after the second dose, all subjects will receive the challenge dose.
- **Treatment allocation**: Following the screening period before the first vaccination (Day -45 to Day -1), subjects will be randomized in a 1:1 ratio to receive either the study vaccine or the placebo.
- **Blinding**: The study will be observer-blind.

Table 3 Blinding of study epochs

Study Epochs	Blinding
Screening (Epoch 001)	N/A
1 st and 2 nd vaccination (Epoch 002)	observer-blind
Challenge (Epoch 003)	observer-blind

Sampling schedule:

- 5 mL for hematology: Screening Visit, Visit 2, Visit 3, Visit 4, Visit 5 and Visit 8. Additionally, hematology is repeated weekly until resolution if neutropenia occurs.
- 5 mL for biochemical analysis: Screening Visit.
- 10 mL for hepatitis B, hepatitis C and HIV: Screening Visit.
- 10 mL for HLA-B27 testing: Screening Visit.
- 5 mL for local anti S. sonnei LPS IgG Screening-ELISA: Screening Visit.
- Urine sample for urinalysis: Screening Visit and Visit 5.
- Urine sample for pregnancy test for women of childbearing potential: Screening Visit, Visit 1, Visit 3, Visit 5 and Visit 8.
- 20 mL for immunological tests (antibody response) at Visit 1, Visit 2, Visit 3,
 Visit 4, Visit 5, 7 days after Visit 5 (Day 64), Visit 6,
- For serum bactericidal activity tests at Visit 1, Visit 3 and Visit 5
- And for Fc glycosylation test on leftover serum samples collected at Visit 1 and Visit 5.
- 50 mL of peripheral venous blood for α4β7+/- plasmablast *analysis by ELISA* and RNA extraction from PBMCs for gene expression profiling: Visit 1, Visit 2, Visit 4 and 7 days after Visit 5 (Day 64). (Amended: 23 July 2019)

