6.7.4.2. Hematology/blood chemistry

Table 12 Hematology/Blood Chemistry read-outs

Blood sampling	g timepoint	No.	Component	
*Type of contact and timepoint Sampling timepoint		subjects	Component	
Screening	Pre-Vacc 1	NA	Hematology Chemistry	
Visit 2 (Day 8)	Post-Vacc 1	72	Hematology	
Visit 3 (Day 29)	Pre-Vacc 2	72	Hematology	
Visit 4 (Day 36)	Post-Vacc 2	72	Hematology	
Visit 5 (Day 57)	Pre-challenge	72	Hematology	
Visit 8 (Day 237)	Post-challenge	72	Hematology	

^{*}Hematology is repeated at 7 and 28 days after each vaccination and repeated weekly until resolution if neutropenia occurs.

Vacc: Vaccination, NA: Not applicable

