9.1.6. Adverse events of special interest

Adverse events of special interest (AESIs) are predefined (serious or non-serious) AEs of scientific and medical concern specific to the product or program, for which ongoing monitoring and rapid communication by the investigator to the sponsor can be appropriate, because such an event might warrant further investigation in order to characterize and understand it.

During the two Phase I studies with the study vaccine, no SAE were reported. Two subjects of African descent experienced a transient and clinically asymptomatic Grade 3 neutropenia (the two episodes were graded as SAEs) that was finally classified as "benign ethnic neutropenia". In addition to these two Grade 3 cases (one in each study), a total of 6 cases of transient and clinically asymptomatic Grade 2 neutropenia (one case in H03_01TP and 5 cases in H03_02TP) has been reported. GVGH has defined neutropenia as AESI. In the phase 2 study in endemic population, there have been 10 cases of neutropenia from 6 subjects of which one was severe, three moderate and 6 mild. All of these events were clinically asymptomatic.

During the course of this study, symptomatic neutropenia will be considered as AESIs.

Table 17 List of potential AESI to be followed during the study

Blood disorders	
Symptomatic neutropenia (all Grades)	

205626 (S SONNEI MONO GMMA SBVGH-003 [H03_03TP]) Protocol Amendment 6 Final

Neutropenia is defined as a decrease of neutrophil count asymptomatically or symptomatically. This is completely diagnosed by laboratory testing for complete blood count. However, only symptomatic neutropenia cases will be considered as AESI and reported as such.

The following grading will be used to classify neutropenia:

- Grade 1: 1800 -1500 cells/μL.
- Grade 2: 1499-1000 cells/μL.
- Grade 3: 999-500 cells/μL.
- Grade 4: $< 500 \text{ cells/}\mu\text{L}$.

In performing their assessment of symptomatic neutropenia cases, investigators are strongly advised to use the table below.

Table 18 Evaluation of symptomatic neutropenia

Common presenting symptoms of neutropenia	Physical findings on examination of a patient with neutropenia		
Low-grade fever	Fever		
Sore mouth	Stomatitis		
Odynophagia	Periodontal infection		
Gingival pain and swelling	Cervical lymphadenopathy		
Skin abscesses	Skin infection: The skin examination focuses on rashes,		
Skill abscesses	ulcers, or abscesses		
Recurrent sinusitis and otitis	Splenomegaly		

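### The hematology safety endpoint omits the Day 29 and Day 57 counts drawn in every subject, which weakens its account of persistence, recurrence and recovery of neutropenia

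*Protocol*

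**What the plan says.** The laboratory endpoint in Section 11.2, repeated in the synopsis, counts out-of-range or clinically significant values "for hematology at 7 days after first and second vaccination and at last study visit (Visit 8". In visit terms these are Visit 2 (Day 8), Visit 4 (Day 36) and Visit 8 (Day 237).

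The sampling schedule in Section 3.2 is wider: "5 mL for hematology: Screening Visit, Visit 2, Visit 3, Visit 4, Visit 5 and Visit 8". Table 4 agrees, and Table 12 in Section 6.7.4.2 lists 72 subjects at each post-dose visit. Its footnote reads "Hematology is repeated at 7 and 28 days after each vaccination and repeated weekly until resolution if neutropenia occurs".

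Section 1.3.1 lists symptomatic neutropenia as the only risk of the investigational vaccine. It describes cases that "have been reported at Day 7 after receipt of the first dose in 5 subjects". It then adds: "One of the 5 subjects had an additional Grade1 neutropenia episode at Day 28". A different subject had a pair of later episodes. The earlier of the pair is given as "one of which was Grade 3 (940 cells/mL) at 7 days after the second dose". For the later of the pair, the table states that "the second was Grade 2 (1,410 cells/mL) at 28 days after second vaccination". The same cell reports eight Phase I cases, all within 20 days of the first dose.

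Under Section 9.1.6 only symptomatic neutropenia is an adverse event of special interest. Under Section 9.1.5 an abnormal laboratory value becomes an adverse event if the investigator judges it clinically significant.

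**The concern.** The protocol singles out neutropenia and schedules a count 28 days after each dose in every subject, yet its laboratory endpoint leaves both of those counts out. The earlier cases are reported as asymptomatic, so the special-interest endpoint would not have counted them. The laboratory endpoint is the only one that counts an abnormal value regardless of symptoms or the investigator's opinion, so its list of visits matters.

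What is at stake is the description of how neutropenia behaves over time: whether a fall seen at Day 8 has recovered by the next dose, whether it recurs, and whether a fall that began after Day 8 is counted at all. This is not hypothetical for this trial. The Amendment 4 rationale in Appendix C refers to neutropenia cases already recorded in it.

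**Working it through.** The plan gives no figure to reproduce here. The check sets the schedule against the endpoint and then places the reported episodes on that timeline.

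**Step 1: visits.** Inputs: Section 11.2 for the endpoint; Section 3.2 and Tables 4 and 12 for the draws.

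| Post-dose draw | Timing | In endpoint? |
|---|---|---|
| Visit 2, Day 8 | 7 days after dose 1 | yes |
| Visit 3, Day 29 | 28 days after dose 1, before dose 2 | no |
| Visit 4, Day 36 | 7 days after dose 2 | yes |
| Visit 5, Day 57 | 28 days after dose 2, before challenge | no |
| Visit 8, Day 237 | last visit | yes |

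The endpoint uses 3 of 5 draws. If all 72 subjects attend every visit, that is 72 × 3 = 216 of 72 × 5 = 360 counts. The other 144 (144/360 = 40%) are collected but lie outside it. After Day 36 its next value is 237 − 36 = 201 days later.

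**Step 2: episodes.** Input: the individually timed episodes in Section 1.3.1, reading the Day 28 episode as 28 days after dose 1.

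- 7 days after dose 1: 5 (Grades 1 and 2)
- 28 days after dose 1: 1 (Grade 1)
- 7 days after dose 2: 1 (Grade 3)
- 28 days after dose 2: 1 (Grade 2)

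Total: 5 + 1 + 1 + 1 = 8 in five subjects. At the omitted times: 1 + 1 = 2, and 2/8 = 25%.

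The eight Phase I cases are a separate set: they were Grade 2 or 3 and within 20 days of dose 1, whereas this series includes Grade 1 and later episodes. Adding them gives 2/(8 + 8) = 2/16 = 12.5%. Section 9.1.6 says of the phase 2 study in an endemic population that "there have been 10 cases of neutropenia from 6 subjects of which one was severe, three moderate and 6 mild". It gives no timing. If the Section 1.3.1 series belongs to that study, at least 2/10 = 20% fell at the omitted times.

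**Step 3: subjects.** All five subjects had an episode at Day 7, a visit the endpoint covers, so 0 of 5 would be missed as ever neutropenic. The subject with the Grade 1 episode at Day 28 already had Grade 1 or 2 at Day 7. The other subject's worst grade, Grade 3, fell 7 days after dose 2, which is also covered. Restricting the visits changes neither the proportion ever affected nor any subject's worst grade in this series. It does remove the evidence that one subject was abnormal again or still at Day 28, and that another was still or again abnormal 28 days after dose 2.

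**Step 4: onset after Day 8.** The Phase I window of 20 days after dose 1 extends beyond Visit 2. A fall beginning after that visit would first be seen on schedule at Day 29. The protocol does not say how many Phase I cases began after the first week, so this part has no number.

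**After the fix:** 5 of 5 scheduled draws, up to 360 counts, and 8 of 8 timed episodes.

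**The case against.** The strongest reply is that nothing is lost from view. An abnormal laboratory finding can be an adverse event (Section 9.1.1). Clinically significant hematology changes are judged against institutional ranges and a published toxicity scale (Section 9.1.5). Adverse events within 28 days of each dose are recorded whatever their intensity (Section 9.3.1) and tabulated by group (Section 11.10). Neutropenia triggers weekly counts until resolution, and post-vaccination hematology goes to the data monitoring committee (Section 6.7.3). The Day 29 and Day 57 draws serve eligibility for dose 2 and challenge, and a schedule with more safety draws than endpoint visits is ordinary. The risk section also supports early sampling: Phase I cases fell within 20 days, and the cited literature places most cases within two weeks.

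Much of this stands. A reader might infer that asymptomatic neutropenia depends wholly on the laboratory endpoint; the adverse-event route shows otherwise. A reader might also infer that the schedule and the endpoint contradict each other; they do not. Nor would rewording a safety endpoint alter who is dosed, challenged or evaluable.

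Two things remain. The adverse-event route passes through the investigator's judgment, whereas the laboratory endpoint also counts values that are simply out of range. And although by-visit tables are usually left to the statistical analysis plan, which is not shown, this protocol does not leave the visits open: it names them, more narrowly than its own schedule. A fuller table would go beyond the stated endpoint.

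**Conclusion.** The point holds as a limited weakness in one descriptive secondary safety endpoint. Two of five scheduled post-dose counts are outside the only endpoint that counts abnormal values irrespective of symptoms or judgment. Between 12.5% and 25% of the earlier episodes fell at those times, depending on whether the Phase I cases are counted. The loss is information on persistence, recurrence and recovery, plus any onset between Days 9 and 28.

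It would be tempting to conclude that the trial will understate how many subjects become neutropenic, or how severely. The protocol's own cases do not support that: 0 of 5 subjects and no worst grade would have been missed. Nor can the two later episodes be read as vaccine effects, because Section 1.3.1 states neither the study nor the arm.

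The conclusion rests on two episodes, on the Day 28 reading above, and on the printed grades. The counts quoted with those grades are given per mL and match the Section 9.1.6 scale only if read per µL. The primary analysis and the sample size are unaffected.

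**What to change.** In Section 11.2 and the synopsis, reword the laboratory bullet to hematology at Visits 2, 3, 4, 5 and 8. Summarise unscheduled repeat counts separately, because only subjects with neutropenia have them and they should not enter the by-visit denominators. Add a table of the worst post-dose neutrophil grade per subject, on the Section 9.1.6 scale, by arm.

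The cost is one reworded bullet, in two places, and one extra descriptive table. The samples are already scheduled. There is no new sampling, no change to the primary analysis and no change to clinical management.
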